Subject Population Key criteria for Inclusion and Exclusion:	
Inclusion Criteria
 
 
1. Adult patients, aged <math>\geq 18</math> years old with a history of laboratory-confirmed SARS-CoV-2 infection via a positive molecular (RT-PCR) or antigen (lateral flow assay) test, receiving outpatient/inpatient care from [name] General Hospital, any time prior to enrollment in this study.
 
2. Patients with/without comorbidities.
 
3. Willing to fill-out online Long COVID symptoms follow-up questionnaire.
 
4. Willing and able to comply with the trial protocol, 6 Minutes Walking Test (re-visits and physical testing).
 
 
Exclusion Criteria
 
 
1. Patients with no registered medical record number (MRN) at [name] General Hospital.
 
2. Refusal to participate in the study or to sign the informed consent form.
 
3. Contraindicated to perform the 6 Minutes Walking Test.
 
4. Patients with no access to a smartphone or computer (desktop, laptop, or tablet) to fill out the online screening questionnaire.
 
5. Patients who died during or before enrollment in the study.
 

Number of Subjects	
A total of 250 subjects are divided into 4 groups according to SARS-CoV-2 vaccination status:
 
 
• Never been vaccinated.
 
• Received 1st dose of vaccination.
 
• Received 2nd dose of vaccination.
 
• Received 3rd dose of vaccination.
 

Study Location	[name] General Hospital, Central Jakarta, Jakarta, Indonesia
Study Duration	Each subject's participation will last for 6 months. The estimated duration for the main protocol is approximately 1 year.
Study Phases	
Screening Screening for eligibility and obtaining consent.
 
Study Examination Online questionnaire filling, 6-Minute Walking Test (6MWT)
 
Follow-up Follow-up examination 3 and 6 months after baseline.

Safety Evaluations	
Adverse events will be monitored and collected by the study team from the point of signed consent until the adverse event(s) are resolved and subjects are stabilized. Adverse events will be managed according to the 6MWT guidelines of the American Thoracic Society (ATS).

---

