Statistical and Analytic Plan	Statistical analyses will be performed using SPSS version 20. Descriptive statistics will describe the incidence of long COVID in participants and its characteristics, the clinical outcome, and the quality of life. The bivariate analysis will be performed using chi-square or fisher , to find the correlation between COVID-19 vaccination status and the characteristics and clinical outcomes of long COVID patients. The value of the limit of significance is 0.05.
Data and Safety Monitoring Plan	If there were any serious adverse events (SAE), the case will be reported to the ethics committee as soon as possible, less than 24 hours from the first time they were discovered, and actions were carried out as quickly as possible until the series of events ends. SAE was written in detail on the SAE form, including the following; when it was first discovered, the manifestation of the incident, the conditions before the incident, the handling of the event, and the outcome.

---

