## STATISTICAL ANALYSIS PLAN

### 1. Randomization

Subjects who meet all inclusion and exclusion criteria will be allocated into four groups; Never been vaccinated, received 1st dose, received 2nd dose, and received 3rd dose of vaccination. Subject allocation will be carried out through block randomization and known only by the pharmacist, and confidentiality is maintained so that subjects, doctors/nurses, researchers, and data analysers do not know the allocation of each subject.

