### 2. Sample Size Calculation

The sample size of this study is obtained from the two-way hypothesis testing formula for the two mean values in two independent groups with a confidence index ( $\alpha$ ) of 95% and power of 80%. Results are considered statistically significant if  $p < 0.05$ . The details of the estimated size of the research subject are as follows:

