#### Analytic study: Prospective Cohort, consecutive sampling method

$$n = \left( \frac{Z_{\alpha}\sqrt{2PQ} + Z_{\beta}\sqrt{P1Q1 + P2Q2}}{P1 - P2} \right)^2 = \left( \frac{1.96\sqrt{2 \times 0.553 \times 0.447} + 0.80\sqrt{0.653 \times 0.347 + 0.453 \times 0.547}}{0.20} \right)^2$$

$$n = 93 \text{ subjects} \rightarrow N = 186 \text{ subjects}$$

Legends:

n : Number of subjects

$Z_{\alpha}$  : Z value in 95% confidence index = 1.96

$Z_{\beta}$  : Z value of test power = 0.80

$P_1 - P_2$  : Minimal difference in proportion considered significant = 0.20 ( $P_1 = 0.653$ )

Q : 1 - P

Assuming a 20% loss to follow-up event, the final sample size is:

$$n = 186 + (186 * 20\%)$$

$$n = 186 + 37$$

$$n = \mathbf{223 \text{ subjects}}$$

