##### **3.2.2. Bivariate analysis**

This analysis is used to see the relationship between the effect of the COVID-19 vaccine on clinical long COVID and the quality of life of long COVID patients. The level of significance used is 0.05. Variables are statistically significant if p-value <0.05. The independent variables in this study are nominal scale, so the test used in this analysis is the chi-square test or fisher's test (in the group of independent variables with a dichotomous scale of 2x2 if the chi-square does not meet the requirements.

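### The SAP calls the vaccination exposure nominal and chooses an unordered test, although number of doses (0 to 3) is ordered; if the four groups are tested together, power is lost for graded dose patterns

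*Combined protocol and SAP*

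**What the plan says.** SAP 3.2.2 (Bivariate analysis) gives its reason for the test: "The independent variables in this study are nominal scale, so the test used in this analysis is the chi-square test". Fisher's test replaces it in 2x2 tables when the chi-square requirements are not met. On the error rate it says: "The level of significance used is 0.05". The synopsis names the same two tests, to be used "to find the correlation between COVID-19 vaccination status and the characteristics and clinical outcomes of long COVID patients".

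The exposure is defined in two places. The synopsis says "A total of 250 subjects are divided into 4 groups according to SARS-CoV-2 vaccination status" and lists never vaccinated, first, second and third dose. SAP section 1 has the same four categories: "Subjects who meet all inclusion and exclusion criteria will be allocated into four groups".

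The sample size in SAP section 2 comes from a "two-way hypothesis testing formula for the two mean values in two independent groups", worked with proportions 0.653 and 0.453. It does not say how four dose groups become two.

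The readable text contains no trend test, ordered dose term or regression model. The figure under SAP 3.2 and the flow diagram in SAP section 4 could not be read.

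**The concern.** None, one, two and three doses form an ordered scale. The SAP's stated reason for choosing chi-square is therefore mistaken for the only exposure the documents define.

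This has two consequences. The Pearson chi-square gives the same p-value if the four dose labels are shuffled, so it cannot show whether outcomes improve as doses increase. It also spreads its power over three degrees of freedom, whereas a trend test puts it on one. If outcomes change gradually with dose, the unordered test is more likely to miss the association. The sample size was derived for two groups, so a four-group comparison has little power to spare.

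**Working it through.** **1. The plan's own figure.** Inputs from SAP section 2: Zα = 1.96, Zβ entered as 0.80 ("Z value of test power = 0.80"), P1 = 0.653, P2 = 0.453, mean P = 0.553.

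- First term: 1.96 × √(2 × 0.553 × 0.447) = 1.378
- Second term: 0.80 × √(0.653 × 0.347 + 0.453 × 0.547) = 0.551
- n = ((1.378 + 0.551) / 0.20)² = 93.0 per group, so 186 in total, and 186 × 1.2 = 223

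The stated 93, 186 and 223 are reproduced. They describe a two-group comparison only.

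**2. Four-group power: assumptions.** The documents do not give these: a binary outcome, all four groups in one 2x4 table, 200 evaluable subjects (250 less 20%), and 0.653 and 0.453 as the extremes of the dose pattern. Alpha is 0.05 two-sided, and groups are equal unless stated.

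**3. Formulas.** Group i has share w, proportion p and score s = 0, 1, 2, 3. The overall proportion is p̄ and the mean score is s̄.

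- Chi-square, 3 df: λ₃ = N Σw(p − p̄)² / [p̄(1 − p̄)], critical value 7.815
- Linear trend, 1 df: λ₁ = N [Σwp(s − s̄)]² / [p̄(1 − p̄) Σw(s − s̄)²], critical value 3.841

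Power is the upper tail of the noncentral chi-square beyond the critical value.

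**4. Linear pattern in full.** Proportions are 0.653, 0.586, 0.520 and 0.453, so p̄ = 0.553 and p̄(1 − p̄) = 0.2472. The weighted squared deviations sum to 0.00556. Then λ₃ = λ₁ = 200 × 0.00556 / 0.2472 = 4.49. Both tests hold the same signal, and the whole difference comes from the degrees of freedom: 40% power on 3 df and 56% on 1 df.

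**5. Other shapes, N = 200, equal groups.**

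| Proportions at 0, 1, 2, 3 doses | λ₃ | λ₁ | Chi-square | Trend |
|---|---|---|---|---|
| Linear | 4.49 | 4.49 | 40.0% | 56.4% |
| Plateau: 0.653, 0.553, 0.453, 0.453 | 5.52 | 4.92 | 48.1% | 60.1% |
| Threshold at two: 0.653, 0.653, 0.453, 0.453 | 8.09 | 6.47 | 66.0% | 72.0% |
| First dose only: 0.653, 0.453, 0.453, 0.453 | 6.00 | 3.60 | 51.8% | 47.5% |
| Third dose only: 0.653, 0.653, 0.653, 0.453 | 6.27 | 3.76 | 53.8% | 49.2% |
| Middle doses only: 0.653, 0.453, 0.453, 0.653 | 8.09 | 0 | 66.0% | 5.0% |

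For the first five patterns, simulation gave values within 2 percentage points of these.

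**6. Sensitivity, linear pattern (chi-square vs trend).**

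- Equal groups: 37% vs 53% at N = 186, and 49% vs 66% at N = 250. For 80% power, N = 486 vs 350.
- N = 200, split 10/10/50/30%: 26% vs 39%.
- N = 200, split 40/20/30/10%: 36% vs 51%.

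**7. Sensitivity, patterns that are unfavourable to trend (N = 200).**

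- Third dose only: 59% vs 49% (10/10/50/30%), 28% vs 19% (40/20/30/10%), 39% vs 22% (20/5/60/15%).
- First dose only: 37% vs 27% (15/35/25/25%).

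**8. An order-restricted alternative.** A two-sided isotonic test with a simulated critical value had more power than the unordered chi-square in every monotone pattern run. By simulation at N = 200 with equal groups, isotonic vs chi-square was 52% vs 41% (linear), 59% vs 53% (first dose only) and 60% vs 54% (third dose only).

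**The case against.** The strongest reply is that a linear trend test is not better for every shape. It loses between 4 and 5 points for a first-dose-only or third-dose-only step with equal groups, and roughly 10 to 17 points under some unequal splits. Dose status is observed, so equal groups cannot be assumed. A middle-doses-only pattern is almost invisible to it. Such patterns are conceivable here: the protocol records vaccine type and date as well as number of doses, and accepts infection at any earlier time. All of this stands, and it is why the unordered test should be kept as a check.

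A reader might infer that the plan states a dose-response hypothesis. It does not. Protocol 5.5 and the objectives expect vaccination to help, without giving a shape across doses. The graded patterns above are assumptions.

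A reader might also infer that a 3-df test of a 2x4 table is definitely planned. SAP 3.2.2 does not say so; it mentions 2x2 tables for Fisher's test, and the sample size compares two groups. If the groups are collapsed, the 3-df figures do not apply. Any loss would then come from the collapsing, which the SAP does not describe. The term nominal is also applied to independent variables in the plural, so it may not be aimed at dose alone.

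Finally, an unordered chi-square on ordered groups is a valid test. That is correct and limits the weight of the point. None of these replies makes nominal the right label for dose number.

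**Conclusion.** The point holds as one of efficiency and interpretation. The SAP gives the wrong scale for its main exposure and uses that scale to select a test that ignores dose order.

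Under the stated assumptions, the cost for a linear pattern is about 16 points of power with equal groups and about 13 to 16 under the unequal splits tried. It is about 12 points for a plateau from two doses and 6 for a threshold at two doses. The size depends on the shape of the dose pattern and the group sizes, and the documents give neither.

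It would be too strong to read this as a flaw in validity: type I error is unaffected. It would also be too strong to conclude that a linear trend test is better whatever the pattern. An ordered analysis does not resolve confounding between self-selected vaccination groups or the two-group sample size. Even with the trend test, power in the linear case is only 56%.

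**What to change.** In SAP 3.2.2 and the synopsis:

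- Describe dose group as ordinal.
- State whether all four groups are compared together and, if not, how they are combined.
- Pre-specify one ordered analysis as the main test of the vaccine association: a linear-by-linear (Cochran-Armitage) trend test, an order-restricted test, or dose number as an ordered regression term.
- Keep the unordered 3-df chi-square, reported as a supportive check for non-linear or non-monotone patterns.

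The choice should be fixed before outcome data are examined. It needs SAP wording only, with no new data or subjects. The price of a linear-score trend test is lower power for single-step effects at the first or third dose and little power for non-monotone patterns. The order-restricted test avoids the single-step loss in the cases run, but has somewhat less power than trend if the pattern is truly linear (52% vs 58% by simulation at N = 200, equal groups).

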#### 5. Methods

##### 5.1. Study Design

This is a prospective cohort, cross-sectional study involving two hundred and fifty (250) subjects of post-acute COVID-19 patients, receiving outpatient/inpatient care from [name] General Hospital during the acute phase of the infection, any time prior to enrollment in this study.

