## 5.2. Study Population and Selection Criteria

All participants will be required to sign a written informed consent, be willing and able to comply with all study requirements, and should meet the following criteria:

1. Adult patients, aged  $\geq 18$  years old with a history of laboratory-confirmed SARS-CoV-2 infection via a positive molecular (RT-PCR) or antigen (lateral flow assay) test, receiving outpatient/inpatient care from [name] General Hospital, any time prior to enrollment in this study
2. Patients with/without comorbidities
3. Willing to fill-out online Long COVID symptoms follow-up questionnaire
4. Willing and able to comply with trial protocol (re-visits and physical testing)

Subjects will be **excluded** from the study based on the following criteria:

1. Patients with no registered medical record number (MRN) at [name] General Hospital
2. Refusal to participate in the study or to sign the informed consent form
3. Any contraindications for 6 Minute Walking Test according to the guidelines of the American Thoracic Society (ATS)
4. Patients with no access to a smartphone or computer (desktop, laptop, or tablet) to fill out the online screening questionnaire
5. Patients who died during or before enrollment in the study

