## 5.4. Data Collection

Data on age, sex, height, weight, body mass index, income, education, comorbidities, smoking, alcohol consumption, documented SARS-CoV-2 vaccination

status (including the amount, type, and when the vaccine was received), detailed history of laboratory-confirmed SARS-CoV-2 infection, Long COVID symptoms, severity, and duration are collected through online screening questionnaire.

Data on quality of life (QoL) are collected through St George's Respiratory Questionnaire (SGRQ) and Short Form (SF)-36 Health Survey self-assessment questionnaire at baseline, 3 and 6 months after enrollment. SGRQ addresses QoL in the domains of symptoms, activity, and impacts within the last 4 weeks; and the SF-36 Health Survey questionnaire addresses QoL in the domains of vitality, physical functioning, bodily pain, general health perceptions, physical and emotional and social role functioning.

Data on functional exercise capacity is measured using the Six-Minute Walking Test (6MWT) at baseline, 3 and 6 months after enrollment. The 6MWT is performed according to the guidelines of the American Thoracic Society (ATS). During the 6MWT, such data are collected: Blood pressure, oxygen saturation (SpO2), heart rate, dyspnea, and overall fatigue score using the Modified Borg scale before and after the test, and also one-time measurement (total distance walked in 6 minutes, symptoms at the end of exercise).

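### The vaccination groups are compared only by an unadjusted chi-square or Fisher test in a non-randomized cohort, and the SAP's block randomization cannot apply to doses already received

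*Combined protocol and SAP*

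**What the plan says.** Protocol section 2.1 makes the effect of vaccination on clinical outcomes and quality of life a primary objective. Two analyses are described in readable text. SAP 3.2.1 is descriptive. SAP 3.2.2 relates vaccination to clinical Long COVID and quality of life: "so the test used in this analysis is the chi-square test", or Fisher's test for 2x2 tables that do not meet the chi-square conditions. The synopsis repeats this. Neither place mentions regression, stratification, matching or weighting.

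On how the groups arise, the documents disagree:

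- Synopsis, Number of Subjects: "A total of 250 subjects are divided into 4 groups according to SARS-CoV-2 vaccination status".
- Protocol 5.1: "This is a prospective cohort, cross-sectional study involving two hundred and fifty (250) subjects of post-acute COVID-19 patients".
- SAP section 2 heads the analytic calculation "Analytic study: Prospective Cohort, consecutive sampling method".
- Protocol 5.4 records the number, type and date of doses by questionnaire, as history.
- SAP section 1, by contrast: "Subject allocation will be carried out through block randomization and known only by the pharmacist", with subjects, clinicians, researchers and analysts all unaware of the allocation.

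Protocol 5.4 also collects possible confounders: "Data on age, sex, height, weight, body mass index, income, education, comorbidities, smoking, alcohol consumption". Protocol 5.2 lets the qualifying infection fall at "any time prior to enrollment in this study".

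**The concern.** Whether someone has had no, one, two or three doses depends on who they are and when they fell ill. Age, sex, BMI, comorbidity, smoking, income and education can each relate both to vaccination and to symptoms, quality-of-life scores or walking distance. Time since infection can do the same, because it is not restricted and symptoms change over time. An unadjusted test attributes all of these differences to the vaccine.

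The error can go either way: a p-value below 0.05 could be read as benefit where there is none, or a real benefit could be hidden. The synopsis expects the results to support vaccination recommendations, so a wrong reading would have consequences. The randomization paragraph makes matters worse, because a reader who trusts it would believe the simple test is protected by design.

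**Working it through.** **1. Can the randomization apply?** The exposure is doses received and dated before or apart from the study (Protocol 5.4). No procedure in the readable text gives a vaccine. Past doses, or their absence, cannot be allocated by a pharmacist. SAP section 1 therefore conflicts with the synopsis, Protocol 5.1 and 5.4, and SAP section 2, and the comparison is observational.

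**2. The plan's own figure.** Inputs from SAP section 2: Z-alpha 1.96, Z-beta 0.80, P1 0.653, P2 0.453, P 0.553.

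n = [(1.96 × 0.7031 + 0.80 × 0.6888) / 0.20]² = 93.04 per group, so 186 in total; 186 × 1.20 = 223. This reproduces. With the normal quantile for 80% power (0.842), n is 96 per group. The formula compares two unadjusted proportions and allows nothing for covariates.

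**3. Illustration of the bias (assumed values, none from the documents).** One binary confounder, no vaccine effect. Let q0 and q1 be its prevalence in unvaccinated and vaccinated, and a and b the outcome risk with and without it. Spurious difference = (q0 − q1)(a − b).

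- Mild: (0.60 − 0.40)(0.65 − 0.45) = 0.04, i.e. 57% vs 53%.
- Strong: (0.70 − 0.30)(0.70 − 0.40) = 0.12, i.e. 61% vs 49%.

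Error rate of the two-sided 0.05 z-test with pooled null variance. Example, strong case, 100 per group: SE under the null = √(2 × 0.55 × 0.45/100) = 0.0704; actual SE = √((0.61 × 0.39 + 0.49 × 0.51)/100) = 0.0698; P(reject) = 1 − Φ((1.96 × 0.0704 − 0.12)/0.0698) ≈ 39.9%.

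| Group sizes | Mild | Strong |
|---|---|---|
| 100/100 | 8.8% | 39.9% |
| 125/125 | 9.7% | 47.9% |
| 62/62 | 7.3% | 26.8% |
| 40/160 | 7.3% | 27.0% |

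**4. What adjustment achieves.** A simulated stratified Mantel-Haenszel test (strong case, 100 per group, 40,000 trials per setting) rejects in 5.1% of trials when the confounder is measured perfectly. With 10% or 20% random misclassification (assumed) it rejects in 10.6% or 20.8%. After standardising on the misclassified confounder, 4.8 or 8.1 of the 12 spurious points remain.

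**5. What adjustment costs for a binary outcome.** Completers: 250 × 0.80 = 200. The variance is multiplied by 1/(1 − R²), an approximation, where R² is the share of vaccination status explained by the covariates. For a 1:1 split with mean confounder prevalence 0.5, R² = (q0 − q1)²: 0.04 mild, 0.16 strong.

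| R² | Power, 100/100, 0.653 vs 0.453 | 95% CI half-width |
|---|---|---|
| 0 | 81.7% | 13.5 points |
| 0.10 | 77.5% | 14.2 |
| 0.16 | 74.6% | 14.7 |
| 0.20 | 72.5% | 15.1 |
| 0.30 | 66.6% | 16.1 |

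Completers per group for 80% power: 96 at R² = 0; 96/0.90, so 107 at 0.10; 96/0.84, so 115 at 0.16. With a 40/160 split, power is about 62% unadjusted and 58% at R² = 0.10.

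**6. Model size.** 200 × (1 − 0.553) = 89 subjects with the less frequent outcome. At an assumed 10 of these per term, about 8 terms fit: any-vs-none plus seven single-term covariates, or three dose terms plus five.

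**The case against.** The best defence of the plan is that part of it is unseen. A figure under SAP 3.2 and the flow diagram in SAP 4 are not shown, and an adjusted step there cannot be excluded. This limits the finding to the readable text. Even so, SAP 3.2.2 and the synopsis name only chi-square/Fisher, and section 1 would still need reconciling. The word correlation in the synopsis is a weak defence when the objectives ask about effect.

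It is also fair that the illustrative error rates rest on invented prevalences and risks, and that 10% to 20% misclassification is implausible for age or sex. The defect does not depend on those figures.

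Three objections to the remedy stand as caveats:

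- **Analysis set.** The figure of 200 completers follows the plan's sizing of all enrolled subjects. The objective, however, concerns Long COVID patients, while eligibility requires only past infection, and SAP section 2 assumes a Long COVID prevalence of 0.40. If only they are compared, 250 × 0.40 × 0.80 = 80 remain. At 40 per group, power is about 43% unadjusted and 40% at R² = 0.10. About 80 × 0.447 = 36 subjects have the rarer outcome, so about 3 terms fit.
- **Scope of the cost.** The power loss and term limit above apply to binary outcomes. For SGRQ, SF-36 and 6MWT, baseline adjustment can improve precision.
- **Exposure timing.** Doses before and after infection, and doses taken during follow-up, raise different questions that covariates alone do not settle.

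**Conclusion.** The concern holds. On the readable text, the planned analysis cannot separate a vaccine effect from differences in who was vaccinated, and the randomization paragraph offers no protection. This follows from the design and needs no numerical assumption. The true size and direction of the bias cannot be derived from the documents; the 4 to 12 points and the 7% to 48% error rates only show what one assumed confounder could do. The cost figures rest on 200 completers, the plan's 0.653 vs 0.453 and the 1/(1 − R²) approximation, and would be much worse if only Long COVID patients are analysed. This must be fixed before analysis, because a primary objective depends on it.

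**What to change.** Required:

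1. Reconcile SAP section 1 with the synopsis, Protocol 5.1 and 5.4, and SAP section 2, so that the documents describe one design.
2. Keep chi-square/Fisher as description.
3. Base the vaccination conclusion on a prespecified adjusted analysis with a short covariate list already collected: for example age, sex, BMI, comorbidity, smoking, and education or income, plus time since infection if the date is captured.
   - For binary outcomes, use regression and preferably also give an adjusted risk difference, since the sizing target is on that scale: "Minimal difference in proportion considered significant = 0.20".
   - For SGRQ, SF-36 and 6MWT, use baseline-adjusted models at 3 and 6 months. Report baseline group differences separately, because earlier doses may already have affected them.
4. State the analysis set, when vaccination status is fixed, and how doses during follow-up are classified. Fit the covariate list to the resulting outcome count.
5. Report estimates with 95% CIs as adjusted associations, and say that residual confounding remains.

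Optional: any-vs-none as the main term, which matches the two-group sizing but collapses the four groups; a dose-number analysis; and a sensitivity analysis separating doses before and after infection.

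The cost is SAP wording, analysis time, and a check that infection date is available from the questionnaire or the medical-record phase in Protocol section 4. No extra visits are needed. For a binary outcome, expect the power loss shown above: about 7 percentage points at R² = 0.16 with 100 completers per group.
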